## **Procedures**

A cohort of 15 children and adolescents with diabetes will be recruited for the study. We hypothesize that glucose concentration collected from interstitial fluid will correlate with both capillary blood glucose (collected from a lancet and measured with a BGMD) and venous glucose (collected from an intravenous

catheter). In this aim, we will measure glucose concentrations collected from children and adolescents with diabetes (type 1 or type 2).

Glucose measurements from all three methods (interstitial fluid - microneedle, capillary blood - lancet, and venous blood - intravenous catheter) will be made simultaneously from each subject every hour from 8:30 AM – 11:30 AM. Suction (up to 500 mmHg) may be applied after microneedle treatment at the skin site for up to 1 hour to withdraw fluid ( $\leq 500 \mu\text{l}$  [microliters]) from the skin. Measurements will be taken every hour for the study period. Subjects will arrive in the morning after an overnight fast and will eat or drink a breakfast during the study visit. Subjects will be asked about the pain and apprehension with each device.

Pain and apprehension will be determined with the use of the visual analog pain scale (VAS) and a questionnaire. Each subject will be asked to rate their apprehension prior to receiving each method for blood or interstitial fluid collection as well as the pain associated with each method immediately after collection. Each subject will receive each method of glucose monitoring simultaneously. Similar to a cross-over study, each subject's apprehension, pain, and glucose with each method will be compared using the paired t-test method. Sample size is determined based on the number of subjects needed to achieve statistically significant differences in pain based on the VAS. In order to detect a pain difference of 20 mm with a standard deviation of 20 at a power of 95% and an alpha of 0.05, 15 subjects will be recruited.

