### Expected Outcomes

In this study, we will develop microneedle patches for collection of interstitial fluid for subsequent measurement of glucose concentration in an effort to improve patient compliance and cost (Fig 1). Recent studies have shown that intradermal microneedle insertion is less painful and strongly preferred by patients receiving drug delivery through injections [13-15]. We hypothesize that interstitial fluid collection using microneedle patches can improve glycemic monitoring in being as effective as conventional methods and in a less painful manner, thereby improving patient compliance. The microneedle patches will be fabricated at the Global Center for Medical Innovation at the Georgia Institute of Technology. Prior to use in human subjects, the microneedle patches will be sterilized by an approved sterility center.

**Fig. 1. Microneedle patches for interstitial fluid glucose monitoring. Prototype patches are shown with green dye in the microneedles for visual enhancement (left). Application of microneedle patches to the skin is simple (center). High magnification images of microneedles (right).**

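### The only analysis named for glucose is a test for a difference in means, which can support neither the correlation claim nor the claim of equal effectiveness

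*Combined protocol and SAP*

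**What the plan says.** The document (combined protocol and SAP) makes two statements about what glucose should show:

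- Procedures: "We hypothesize that glucose concentration collected from interstitial fluid will correlate with both capillary blood glucose" and with venous glucose.
- Expected Outcomes: the patch "can improve glycemic monitoring in being as effective as conventional methods and in a less painful manner".

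One sentence under Procedures covers the analysis of all three outcomes. Along with apprehension and pain, each subject's "glucose with each method will be compared using the paired t-test method". In the text available, this is the only statistical method named for glucose. There is no correlation analysis, agreement analysis, accuracy criterion or equivalence margin, and no statement of how a significant or a non-significant glucose result would be interpreted.

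The sample size rests on pain: "Sample size is determined based on the number of subjects needed to achieve statistically significant differences in pain based on the VAS". Glucose is to be measured by all three methods hourly from 8:30 to 11:30 AM, which is up to four readings per child and method if both ends count. The plan does not say how these readings enter the t-test.

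**The concern.** Pain and glucose share a test, but their hypotheses point in opposite directions. For pain the sponsor hopes to show a difference, and a paired t-test suits that. For glucose the sponsor hopes to show that the patch reads like the lancet and the venous sample. The t-test takes equality of means as its null hypothesis and looks for evidence against it, so failure to reject leaves the question open. Nor does the test measure correlation: two methods can be perfectly correlated and differ in mean, or have equal means and be unrelated.

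Two errors become possible. A biased and noisy patch may show no significant difference, and a precise patch with a trivial bias may show a significant one. The Background says that children need glucose readings to adjust diet and drug treatment, so an unsupported statement that the patch performs as well as existing methods would matter. The stated 95% power gives no protection here, because it belongs to the pain comparison.

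**Working it through.** **Inputs from the document (Procedures).** 15 children, each receiving all three methods; paired t-test; alpha 0.05 (taken as two-sided, since sidedness is not stated); pain difference 20 mm, SD 20, power 95%.

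**Inputs assumed.** The document gives no glucose bias, SD or margin. I use a true mean bias of 15 mg/dL, SDs of the within-child difference from 15 to 40 mg/dL, and a margin of 15 mg/dL. These values are illustrative only.

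**Step 1: the plan's own figure.** Take SD 20 as the SD of paired differences. The noncentrality is (20/20) × √15 = 3.87, with 14 degrees of freedom and critical value 2.145. Exact power is 94.9%, against 95% stated. The figure of 15 reproduces, for pain only.

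**Step 2: chance of a non-significant glucose t-test, one difference per child.** P(non-significant) = P(|T| < 2.145), where T is noncentral t with 14 df and noncentrality (bias/SD) × √15.

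| SD of differences (mg/dL) | Noncentrality at bias 15 | P(non-significant), bias 15 | P(non-significant), bias 0 |
|---|---|---|---|
| 15 | 3.87 | 5% | 95% |
| 20 | 2.90 | 23% | 95% |
| 30 | 1.94 | 56% | 95% |
| 40 | 1.45 | 73% | 95% |

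With a fixed non-zero bias, the noisier device is likelier to show no significant difference. With zero bias the rate is 95% at every SD, so the test is blind to individual errors that cancel on average. At a bias of 10 the pattern is the same: 5%, 56% and 85% at SD 10, 20 and 40.

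**Step 3: allowing for hourly readings.** If four differences per child are averaged (an assumption), the SD of the child mean is SD × √((1 + 3ρ)/4), where ρ is the within-child correlation of the differences. At SD 30 and bias 15:

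- ρ = 0: 30 × √(1/4) = 15.0, so P(non-significant) = 5%.
- ρ = 0.5: 30 × √(2.5/4) = 23.7, so P(non-significant) = 37%.

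The 56% in Step 2 is therefore the upper end for this design. The direction does not change.

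**Step 4: an equivalence interval for comparison.** Two one-sided 5% tests, equivalent to requiring the 90% interval to lie inside ±15, simulated with n = 15 and one difference per child:

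- True bias 15 (at the margin): passes at most about 5% of the time at every SD.
- True bias 0: passes 96%, 74%, 20% and 3% of the time at SD 15, 20, 30 and 40.

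Here more noise makes a favourable result less likely, as it should.

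**Step 5: why the mean alone is not enough.** At zero bias and SD 15 the patch passes Step 4 96% of the time, yet about 95% of individual differences then span ±1.96 × 15 = ±29 mg/dL. Individual readings must be examined too. With n = 15 and one pair per child, the 95% confidence interval of each limit of agreement is about ± 2.145 × √(1/15 + 1.96²/28) = ±0.97 SD.

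**The case against.** The strongest reply is that a reader might infer a rule that a non-significant t-test means the patch is as good as the other methods. The document never states that rule. Procedures says only that glucose will be compared, and a paired t-test can be reported with a mean difference and an interval. This stands: the reversed burden of proof is a risk left open by the plan, not a declared decision rule. It does not rescue the plan, because neither outcome of the named test can establish correlation or similarity, and no other analysis is given.

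A reader might also infer that noise always helps the patch. It does so only when a true mean bias exists; at zero bias the rate stays at 95%.

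The sizes can be challenged as well. Bias, SD and margin are all assumed, and one value per child ignores the hourly readings, which would lower the rates (Step 3). This stands, and the figures should be read as showing direction.

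Finally, this is a 15-child first assessment of prototype patches, and the document openly ties its sample size to pain, so the power is not misrepresented. The paired data could also be analysed for agreement with no change in conduct. These points bear on severity. They do not make the t-test suitable.

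**Conclusion.** Wrong as written; should be fixed. This is a mismatch between method and claim, not a missing detail: the one analysis named for glucose tests for a difference in means, while the claims are correlation and equal effectiveness.

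The size of the problem cannot be fixed from the document. Under the assumptions above (bias 15 mg/dL, one difference per child), non-significance has probability 5% to 73% as the SD goes from 15 to 40. Averaging four readings brings the SD 30 figure down from 56% to between 5% and 37%, for within-child correlations of 0 to 0.5. The conclusion itself does not depend on these values. The pain sample size is not in question on this point.

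**What to change.** Keep the paired t-test for pain and apprehension. For glucose, replace it with a prespecified agreement analysis of the paired readings, interstitial minus capillary and interstitial minus venous:

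1. The mean difference with a 90% confidence interval, judged against a margin fixed before the first child is studied.
2. Limits of agreement with confidence intervals, so that individual errors that average out are visible.
3. Both computed by a method that allows for the repeated hourly readings within child.

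State also whether one or both comparators must meet the criterion, that a non-significant difference will not be read as agreement, and that the 95% power applies to pain only.

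The cost is a short analysis section and an agreed margin, with no extra children or measurements. The downside is that the glucose result may be inconclusive at n = 15: at an assumed margin of 15, with one pair per child, an unbiased patch would meet the mean criterion only 20% of the time at SD 30. Reporting that as inconclusive would be accurate.

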### Expected Outcomes

In this study, we will develop microneedle patches for collection of interstitial fluid for subsequent measurement of glucose concentration in an effort to improve patient compliance and cost (Fig 1). Recent studies have shown that intradermal microneedle insertion is less painful and strongly preferred by patients receiving drug delivery through injections [13-15]. We hypothesize that interstitial fluid collection using microneedle patches can improve glycemic monitoring in being as effective as conventional methods and in a less painful manner, thereby improving patient compliance. The microneedle patches will be fabricated at the Global Center for Medical Innovation at the Georgia Institute of Technology. Prior to use in human subjects, the microneedle patches will be sterilized by an approved sterility center.

**Fig. 1. Microneedle patches for interstitial fluid glucose monitoring. Prototype patches are shown with green dye in the microneedles for visual enhancement (left). Application of microneedle patches to the skin is simple (center). High magnification images of microneedles (right).**

